- 9 Diffusion tensor imaging (DTI) is an MRI technique which characterizes the magnitude, anisotropy and orientation of the diffusion tensor, using the pulsed-gradient, spin echo pulse sequence with a single-shot, echo planar imaging readout. DTI data will be obtained using whole brain coverage, a maximum of 2.5 mm isotropic resolution and at least 30 diffusion encoding directions and may be obtained using either a 1.5 or 3 Tesla MRI scanner. DTI is required for subjects at assessment sites with DTI capability. DTI is optional for sites without access to DTI-compatible scanners. Perfusion imaging is also required for subjects at assessments sites when the MRI has the capacity.
- 10 All efficacy assessments will be completed solely by blinded study personnel that do not have access to patient study safety information (this includes adverse events, concomitant medications, progress notes, and MRI reports).
- 11 The mRS Screening value is to be recorded by the clinical site utilizing the IXRS.
- 12 The subject global rating of perceived change should be completed by the subject. In the event the subject is not able to complete the questionnaire, the caregiver will be allowed to ask the questions of the subject and complete the questionnaire using the subject's answer(s).
- 13 Subjects will undergo study surgical procedure on Day 1 only after all other procedures for this visit have been completed.
- 14 Subjects will be discharged on Day 2 unless complications require a longer stay.
- 15 Adverse event collection begins from the time Informed Consent is provided.
- 16 During the surgical visit, adverse events and concomitant medications will be recorded pre- and post-surgery.
- 17 Including prior and concomitant medications at Screening.

Table 3: Schedule of Assessments (Continued)

Study Period	Follow-up	
Study Visit Type	Assessment	
Study Visit	9	10/ Early Termination
Study Day	252 (± 14)	336 (± 14)
Study Week	36	48
Study Month	9	12
Pregnancy Test ¹		X
Physical Exam		X
Physical Therapy Instruction and Subject Exercise Diary given to subject	X	
Subject Exercise Diary Review	X	X
Leg Activity Monitor Given to Subject	X	
Leg Activity Monitor Collected from Subject	X	X
Vital Signs	X	X
Chest X-Ray and ECG		X
Hematology	X	X
Serum Chemistry	X	X
INR		X
Serum for anti-HLA Antibodies ²		X
PBMC ²		X
Imaging--Head MRI ³		X
Imaging – Diffusion Tensor Imaging ⁴		X
Modified Rankin Score (mRS) ⁵	X	X
Fugl-Meyer Motor Score (FMMS) ⁵	X	X
Action Research Arm Test (ARAT) ⁵	X	X

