11.0 TREATMENT ASSIGNMENT AND BLINDING

This is a double-blind study. Subjects will be randomized in a 1:1:1 ratio via an IXRS, stratified by Screening mRS score. Each subject will be randomized at a surgical site prior to the surgical procedure after study eligibility is confirmed. The randomization will be balanced, in terms of numbers of subjects between the treatment groups, within each surgical site.

The blind will be maintained by role definition and procedures described below:

Unblinded personnel:

- Cell preparation staff
- Unblinded study coordinator
- Surgeon and Operating Room staff
- Designated unblinded sponsor & clinical research organization (CRO) personnel
- Data and Safety Monitoring Board (DSMB) members and the supporting statistician and programmer involved in regular review and generation of unblinded safety data

Blinded personnel:

- Assessment site staff
- Designated blinded sponsor & CRO personnel

In order to maintain the blind the following procedures will be implemented:

1. Unblinded cell preparation staff will prepare and perform a quality check of the cell suspension for each subject. The identity of the treatment will be concealed by the preparation of study product that is identical in packaging, labeling, schedule of administration, administration, and appearance.
2. The neurosurgeon and Operating Room (OR) staff will perform the sham surgery procedure using a surgical script that mimics the cell administration procedure as closely as possible (e.g. sequence of steps and overall time taken in the OR).
3. Subjects, assessment site staff, persons performing the assessments, blinded sponsor staff, and blinded CRO staff will remain blind to the identity of the treatment from the time of randomization until database lock and unblinding, using the following methods:
 - a. Randomization data are kept strictly confidential until the time of unblinding, and will not be accessible by any of the blinded study personnel in the study, unless subject level emergency unblinding is required as noted in section 11.1 Emergency Unblinding Procedures.

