15.10 Clinical Stroke Evaluations

Detailed information regarding clinical stroke evaluations (including sample forms and instructions for conducting the evaluations) will be provided separately from this protocol.

Fugl-Meyer Motor Score (FMMS)

FMMS will be calculated as change from baseline for Months 1, 3, 6 (primary), 9 and 12. The treatment group will be compared to the control group based on the relative proportion of subjects who improve at least 10 points.

Modified Rankin Scale (mRS)

The mRS will be calculated to determine eligibility (mRS 2-4) at screening and again at Baseline, Months 1, 3, 6 (secondary), 9 and 12 months. The treatment group will be compared to the control group based on based on the relative proportion of subjects who improve at least

1 point. The mRS for all assessments except the Screening assessment will be recorded on video and reviewed in a blinded fashion by a central external rater.

Motricity Index

To ensure subjects have a defined motor deficit, an assessment of the subject's Motricity Index will be calculated at Screening for study eligibility purposes. Subjects will require either Motricity Index 30-75 (Upper Extremity Scale) OR 27-74 (Lower Extremity Scale).

Action Research Arm Test (ARAT)

ARAT scores will be calculated at Baseline and Months 1, 3, 6 (secondary), 9 and 12. The treatment group will be compared to the control group based on the relative proportion of subjects who improve at least 6 points.

Gait Velocity

Gait Velocity on a standard 10 m walk will be calculated at Baseline and Months 1, 3, 6 (secondary), 9 and 12. The treatment group will be compared to the control group based on the relative proportion of subjects who improve at least one functional level (e.g. from <0.4 m/s to 0.4-0.8 m/s or from 0.4-0.8 m/s to >0.8 m/s).

NeuroQOL

Two subdomains of the NeuroQOL will be assessed at Baseline and Months 1, 3, 6 (secondary), 9 and 12 using the Short Forms. The 2 subdomains include: Upper Extremity Function (Fine motor ADL) and Lower Extremity Function (Mobility). The treatment group will be compared to the control group based on the mean change in T Scores from baseline.

Global Rating of Perceived change from Baseline

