3.6. TREATMENT ASSIGNMENT & BLINDING

This is a double-blind study. After study eligibility is confirmed, subjects will be randomized in a 1:1:1 ratio via an IXRS, stratified by Screening mRS score of 2, 3 and 4. Each subject will be randomized at a surgical site on the morning of the day of surgery (i.e. approximately 2-3 hours before surgery). The randomization will aim to be balanced, in terms of numbers of subjects between the treatment groups, within each surgical site.

Unblinded cell preparation staff will prepare and quality check the cell suspension for each subject per written procedures, randomization assignment, and other applicable local regulations as set forth in the protocol.

The neurosurgeon and or surgical staff will be unblinded. The sham surgery procedure will be scripted to mimic the cell administration procedure as closely as possible.

Subjects, investigator, staff, persons performing the assessments, sponsor, data analysts, and personnel at clinical and imaging core laboratories will remain blind to the identity of the treatment from the time of randomization until database lock and unblinding, using the following methods: randomization data are kept strictly

INC1005439

Sponsor: SanBio, Inc.

Protocol: SB-STR02

Final 1.0

Statistical Analysis Plan

confidential until the time of unblinding, and will not be accessible by anyone else involved in the study. MRIs will be over-read by a central reader post-surgery and blinded imaging reports will be sent to the assessment site staff.

The following are the exceptions to those staff required to remain blinded: DSMB members, including the unblinded statistician and programmers from the statistical service provider, individuals involved in regular review of safety data, clinical data, imaging service provider, unblinded cell preparation staff, unblinded neurosurgeon and OR surgical staff, and unblinded study monitor.

The blinded treatment assignment/dose information is to be broken only in an emergency when knowledge of such treatment may have an impact on further treatment decisions or aid in the emergency treatment of the subject. The Investigator will obtain the treatment assignment for the specified subject by accessing the IXRS. Date and reason for unblinding are to be promptly communicated via telephone and in writing to the Medical Monitor and documented in the CRF.

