5.3. PER PROTOCOL POPULATION

The Per Protocol (PP) population will include all subjects in the mITT population who do not have important protocol deviations. Important protocol deviations are detailed in Section 6 below.

All efficacy analyses will utilize mITT population. The primary and selected secondary endpoints will also be analyzed using the Per Protocol population as a sensitivity analysis.

INC1005439

Sponsor: San-Bio, Inc.

Protocol: SB-STR02

Final 1.0

Statistical Analysis Plan

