9. EFFICACY

Descriptive summary statistics will be presented for actual measurement values and for changes from baseline by visit for the continuous variables. Number and percent of subjects will be summarized for each visit for the categorical variables.

Generalized Linear Mixed Model (GLMM) will be used for analysis of the primary endpoint FMMS response rate and the secondary endpoints mRS/ARAT/Gait Velocity/global ratings of perceived change response rate. Adjusted odds ratios and 95% confidence intervals (CIs) will be reported for the comparison of combined SB623 group versus sham control and separately for the comparisons of each SB623 group versus sham control.

Mixed Model for Repeated Measures (MMRM) analysis will be used to analyze continuous variables with more than one post-baseline assessment, whereas Analysis of Covariance (ANCOVA) will be used for continuous variables with one post-baseline assessment.

All efficacy analysis will be performed on the mITT population. The primary (FMMS response) and the key secondary endpoint (mRS) will be performed on the per protocol population as well. Details are given in Sections 9.1 and 9.2 below.

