A GLMM model will be utilized using the mITT population as primary analysis. The GLMM model will have the outcome variable, FMMS responder (either \geq or $<$ 10 points improvement in FMMS), and independent variables of treatment, visit, treatment and visit interaction, and pooled surgical site as effects, and baseline FMMS motor total score and baseline mRS score as covariates. Treatment, visit, and pooled surgical site will be treated as categorical variables. Visit will be fitted as a repeated effect within subject. Link function will be set to logit and distribution to binary. An unstructured variance-covariance structure will be used. If this fails to converge then the following variance-covariance structures will be used based on the step-down order until model convergence is obtained: heterogeneous Toeplitz, heterogeneous autoregressive, heterogeneous compound symmetry, and then compound symmetry. The Kenward-Roger method will be used to estimate the denominator degrees of freedom. Adjusted odds ratios and 95% CIs for each visit will be presented for combined SB623 versus sham control. A separate analysis will be repeated for the comparisons of each SB623 group versus sham control for FMMS response. A forest plot of odds ratios and 95% CIs will be presented for individual/combined SB623 versus sham control. The results for Month 6 will be the primary interest.

For FMMS response, a supportive analysis will also be conducted based on the per protocol population using the same statistical method and following the same process for selection of variance-covariance structure.

A logistic regression analysis will be conducted by visit to include FMMS response as outcome variable, and independent variables of treatment and pooled surgical site as effects, and baseline FMMS motor total score and baseline mRS score as covariates. Odds ratios and 95% CIs will be reported for each visit.

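### Does leaving the randomisation stratum (Screening mRS) out of every analysis of FMMS response weaken the primary result?

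*SAP*

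**What the plan says.** SAP 3.6 states that randomisation is "stratified by Screening mRS score of 2, 3 and 4". Protocol 9.1, Table 3 footnote 11, gives the source of that value: "The mRS Screening value is to be recorded by the clinical site utilizing the IXRS". Protocol 15.10 has the mRS at all assessments "except the Screening assessment will be recorded on video and reviewed in a blinded fashion by a central external rater". SAP 7.2.1 takes the last value before surgery as baseline. mRS is repeated at Visit 2, so Baseline mRS is normally a different rating from the stratum. The two coincide by rule only if the Visit 2 value is missing.

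SAP 9.1.1 plans three model-based analyses of FMMS response:

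- the primary GLMM, with pooled surgical site, baseline FMMS and Baseline mRS;
- a per-protocol repeat: "a supportive analysis will also be conducted based on the per protocol population using the same statistical method" (SAP 5.3 says that the endpoints concerned "will also be analyzed using the Per Protocol population as a sensitivity analysis");
- a logistic regression at each visit, with "independent variables of treatment and pooled surgical site as effects, and baseline FMMS motor total score and baseline mRS score as covariates".

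The mRS subgroup in SAP 9.3 also uses Baseline mRS. On the effect measure, SAP 9 says: "Adjusted odds ratios and 95% confidence intervals (CIs) will be reported for the comparison of combined SB623 group versus sham control". Surgical site is a second balancing factor; Protocol 11.0 says: "The randomization will be balanced, in terms of numbers of subjects between the treatment groups, within each surgical site".

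**The concern.** The usual expectation is that the analysis reflects the randomisation. Here the stratum and the covariate share a name but are two ratings: one by the site up to 84 days before surgery, the other later and centrally reviewed. The supportive analyses change the population or the use of repeated visits, but all keep the same covariates and site terms. A reader might therefore fear that the result hangs on that set and that nothing planned would show it. About 36 responders are expected (0.33 x 92 = 30.4 plus 0.117 x 46 = 5.4), beside up to about 10 site terms. The hypothesis and sample size are also stated in proportions, while only odds ratios are given confidence intervals. If the omission distorted the test, the type I error or power of the primary comparison would be at stake.

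**Working it through.** **1. The planned size.** Inputs from SAP 3.5: 33% vs 11.7%, two-sided 0.05, 80% power, 2:1.

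n(sham) = [1.96 x sqrt(1.5 x p(1-p)) + 0.8416 x sqrt(pc(1-pc) + pt(1-pt)/2)]^2 / (pt-pc)^2

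- p = (2 x 0.33 + 0.117)/3 = 0.259
- first term: 1.96 x sqrt(1.5 x 0.1919) = 1.0516
- second term: 0.8416 x sqrt(0.1033 + 0.1106) = 0.3892
- n(sham) = 1.4408^2 / 0.213^2 = 45.8, so 46 sham, 92 treated and 138 in all, as stated

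This calculation uses no strata, so the planned power does not depend on adjusting for one.

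**2. Direction of the error if mRS were ignored altogether.** With blocks inside a prognostic stratum, an unadjusted test errs on the conservative side. Simulated type I error with 138 subjects ran from 5.1% down to about 2.7%. The lowest value came with an odds ratio of 5 per mRS grade and equal strata. The SAP is not in this position, because it adjusts for Baseline mRS.

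**3. Baseline mRS in place of the stratum.** Assumptions: strata 15/55/30%; response driven by Screening mRS; blocks of 3 within stratum; 3,000 trials per setting (95% simulation error about 0.8 points for alpha). Logistic score tests with linear Baseline mRS or the categorical stratum, without FMMS or site terms:

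| Odds ratio per grade | Agreement | Alpha, Baseline mRS | Alpha, stratum | Power, Baseline mRS | Power, stratum |
|---|---|---|---|---|---|
| 2 | 60% | 4.7% | 5.1% | 82.9% | 84.0% |
| 2 | 80% | 5.3% | 5.4% | 82.8% | 84.2% |
| 3 | 60% | 5.2% | 5.6% | 82.0% | 84.7% |
| 3 | 80% | 4.8% | 5.2% | 84.1% | 85.3% |
| 5 | 60% | 3.5% | 4.4% | 83.0% | 86.5% |
| 5 | 80% | 5.0% | 4.9% | 85.8% | 87.5% |

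At 100% agreement the two differ by at most 0.2 points. With Baseline mRS there is no inflation beyond simulation error. The largest power loss is 86.5 - 83.0 = 3.5 points, at odds ratio 5 and 60% agreement, and power stays above 80%.

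**4. Where the alpha contrast comes from.** A Cochran-Mantel-Haenszel (CMH) test by Screening mRS does sit closer to 5% than the planned logistic regression. To see why, change one element at a time (N = 138, 11 site levels, assumed inputs):

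| Test at Month 6 | Alpha, 26% in both arms | Alpha, 11.7% in both arms |
|---|---|---|
| Planned by-visit logistic | 5.5-6.0% | 4.8-6.0% |
| Same, without site terms | 4.2-5.0% | not run |
| CMH by Screening mRS | 4.8-5.2% | 4.2-5.8% |
| CMH by Baseline mRS | 4.4-5.3% | not run |

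Dropping the site terms and keeping Baseline mRS removes the excess. Swapping one mRS for the other within CMH changes little. In a wider grid of 64 settings, adding the stratum to the SAP's logistic model gave 4.9-7.1%, against 3.4-6.5% without it. The stratum is not what brings alpha down. The 26% null is the pooled planned rate. If the cells did nothing, the sample-size assumption would put both arms at the sham rate of 11.7%, where the two tests largely overlap.

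**5. The scale of the effect.** In a randomised comparison with a common odds ratio, an odds ratio of 1 means equal proportions, so the planned test addresses the stated hypothesis. Table 14.2.1.1 and Figure 14.2.1.12 report responders by arm, and a crude difference follows from them. At the planned rates, SE = sqrt(0.33 x 0.67/92 + 0.117 x 0.883/46) = 0.0682, so the difference is 21.3 points with a 95% CI of 7.9 to 34.7.

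**The case for a change.** The strongest case is that the gap is real, the remedy cheap, and a check fixed before unblinding more credible than one added later. One stratified test and a risk difference would need no new data. Over the 64 settings, alpha exceeded 5.5% in 36 for the planned logistic regression and in 2 for the CMH test. The two tests disagreed in 5.9-10.8% of trials under the alternative.

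The textual facts stand: no planned analysis of FMMS response uses the IXRS value, and no risk difference with an interval is named. It also stands that a Wald logistic regression with many site terms and about 36 responders can be slightly liberal. The rest does not carry the point:

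- That logistic regression is itself supportive. A small alpha difference between two supportive analyses changes no decision.
- The 64 settings give baseline FMMS no effect of its own, which favours CMH; there its power was 0.9 points lower to 6.2 points higher. With FMMS prognostic (32 settings) the range was 5.4 lower to 4.9 higher.
- Disagreement runs both ways. Under the null the logistic regression alone was significant in 0.7-3.6% of trials; in separate runs CMH alone was significant in 1.4-2.4%. Without a rule for reading a disagreement, the extra test can add ambiguity.
- CMH by Screening mRS drops surgical site, the other balancing factor, so it does not follow the full randomisation either.

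**Conclusion.** The concern does not hold. Adjusting for a centrally reviewed mRS taken before randomisation, in place of the site-entered stratum, leaves the comparison valid. It costs at most about 3.5 points of power under extreme assumptions. The alpha contrast that seemed to favour a stratified test belongs to the site terms and shrinks at the 11.7% sham rate. In the 11-site runs, power of the logistic regression and of CMH by Screening mRS was within about 2 points. Following the SAP as written gives a sound conclusion; an added CMH test or risk difference is optional reporting.

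The documents give no stratum sizes, no agreement between Screening and Baseline mRS and no prognostic strength, so these are assumed. The 11 site levels are also assumed: the 4 pooled sites in SAP Table 3 plus the 7 site numbers from 501 to 519 not listed there. The repeated-visit GLMM with Kenward-Roger degrees of freedom was not simulated, so these figures do not establish its exact alpha or power.

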9.1.2. FMMS Score - Additional Analysis

An additional analysis using mixed model for repeated measures (MMRM) will be performed treating the change from baseline in FMMS motor total score as a continuous outcome (dependent) variable. The independent variables will be treatment, visit, treatment-by-visit interaction, and pooled surgical site as effects, and baseline FMMS motor total score and baseline mRS score as covariates. Treatment, visit, and pooled surgical site will be treated as categorical variables. Visit will be fitted as a repeated effect within subject. The analysis will be carried out using a restricted maximum likelihood (REML) based repeated measures approach. An unstructured variance-

Statistical Analysis Plan

covariance matrix will be used. If this fails to converge then the following variance-covariance structures will be used based on the step-down order until model convergence is obtained: heterogeneous Toeplitz, heterogeneous autoregressive, heterogeneous compound symmetry, and then compound symmetry. The Kenward-Roger method will be used to estimate the denominator degrees of freedom. Means and least-squares means (LS-mean) by treatment group and visit, along with the SE of LS-mean for the change from baseline measurement will also be displayed. Treatment comparisons will be displayed showing the treatment difference LS-mean and the 95% confidence limits of the treatment differences along with the p-value for the comparison of combined SB623 versus sham control and separately for the comparisons of each SB623 group versus sham control for each visit. Significance tests will be based on LS Means using Type III sum of squares

These additional analyses for FMMS motor total score will be repeated for the UE-FMMS and LE-FMMS subscale scores indicated in Section 9.1.1

9.2. SECONDARY EFFICACY ENDPOINTS AND ANALYSES

9.2.1. mRS Response

mRS data will be scored as described below:

- 0 - No symptoms.
- 1 - No significant disability. Able to carry out all usual activities, despite some symptoms.
- 2 - Slight disability. Able to look after own affairs without assistance, but unable to carry out all previous activities.
- 3 - Moderate disability. Requires some help, but able to walk unassisted.
- 4 - Moderately severe disability. Unable to attend to own bodily needs without assistance, and unable to walk unassisted.
- 5 - Severe disability. Requires constant nursing care and attention, bedridden, incontinent.
- 6 - Dead.

The proportion of SB623 treated subjects (pooling both SB623 doses) and sham that improve at least 1 point on mRS from Baseline will be analyzed for each time point using a GLMM model that will include treatment, visit, and treatment-by-visit, and pooled surgical site as fixed effects, and baseline mRS score as a covariate. Percent of subjects will be presented graphically by scores of 0-1, 2-3, 4-5 and 6.

Number and percentage of subjects in mRS will be tabulated for the following change categories:

- ≤ -2 (Better)

Statistical Analysis Plan

- -1
- 0
- 1
- ≥ 2 (Worse)

The analysis will be repeated by the comparisons of each SB623 group versus sham control for each visit.

